6.4. Study Intervention Compliance

When study intervention is administered as an IV infusion or SC injection by qualified staff, the details of each administration will be recorded in the eCRF. For IV infusions, this will include date and start and stop times of the IV infusion and volume infused; for SC injections, this will include date and time of SC injection.

Participants will receive instructions on compliance with study intervention when they begin self-administration of study intervention at home. When participants begin self-administration at home, the investigator or designated study personnel will maintain a log of all study intervention dispensed and returned.

When study intervention is self-administered by participants at home, participants will record all study interventions on a diary card.

Additional details may be provided in the site IPPM and IPPI that is provided separately. Compliance with the treatment schedule is strongly encouraged.

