7.1.1. Conditions That Require Study Intervention Discontinuation

A participant's study intervention must be discontinued under the following conditions:

1. The participant (or the participant's representative) withdraws consent to receive study intervention.
2. The investigator believes that for safety or tolerability reasons (eg, adverse event), it is in the best interest of the participant to discontinue study intervention.
3. The participant becomes pregnant or plans a pregnancy within the study period. Refer to Appendix 6 (Section 10.6), Contraceptive and Barrier Guidance and Collection of Pregnancy Information.
4. The participant initiates treatment with prohibited therapies for UC (Section 6.5.2).
5. The participant has a colectomy.
6. The participant develops an opportunistic infection.
7. The participant is deemed ineligible according to the following TB screening criteria:

A diagnosis of active TB is made.

A participant has symptoms suggestive of active TB based on follow-up assessment questions and/or physical examination or has had recent close contact with a person with active TB and cannot or will not continue to undergo additional evaluation.

A participant undergoing evaluation has a chest radiograph with evidence of current active TB and/or a positive QuantiFERON-TB[®] (or T-SPOT[®] for sites in Japan) test result (and/or a positive tuberculin skin test result in countries/territories in which the QuantiFERON-TB[®] test is not approved/registered or the tuberculin skin test is mandated by local health authorities), unless active TB can be ruled out and appropriate treatment for latent TB can be initiated prior to the next study intervention administration and continued to completion (see also Section 8.2.11 and Appendix 5 [Section 10.5]). Indeterminate QuantiFERON-TB[®] (or borderline T-SPOT[®] for sites in Japan) test results should be handled as described in Section 8.2.11. Participants with persistently indeterminate QuantiFERON-TB[®] (or borderline T-SPOT[®] for sites in Japan) test results may continue without treatment for latent TB if active TB is ruled out, their chest radiograph shows no abnormality suggestive of TB (active or old, inactive TB) and the participant has no additional risk factors for TB as determined by the investigator. This determination must be promptly reported to the medical monitor or designee and recorded in the participant's source documents and initialed by the investigator.

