Note: In Ukraine, while the QuantiFERON-TB® test is not approved/registered, it is acceptable, and an additional tuberculin skin test is not required.

A participant receiving treatment for latent TB discontinues this treatment prematurely or is noncompliant with the therapy.

8. The participant has a serious adverse reaction that is related to an injection or an infusion resulting in bronchospasm with wheezing and/or dyspnea that requires ventilatory support **OR** that results in symptomatic hypotension with a decrease in systolic blood pressure >40 mm Hg or blood pressure <90/60 mm Hg.
9. The participant has a reaction resulting in myalgia and/or arthralgia with fever and/or rash (suggestive of serum sickness and not representative of signs and symptoms of other recognized clinical syndromes) occurring 1 to 14 days after an injection of study intervention. These may be accompanied by other events including pruritus, facial/hand/lip edema, dysphagia, urticaria, sore throat, and/or headache.
10. The participant has a malignancy including squamous cell skin cancer. Consideration may be given to allowing participants who develop ≤ 2 basal cell skin cancers that are adequately treated with no evidence of residual disease to continue to receive study intervention.
11. The participant has severe liver test abnormalities that are not transient and are not explained by other etiologies, as described in Section 8.2.4 and Appendix 9 (Section 10.9; Guideline Algorithm for Monitoring, Assessment, and Evaluation of Abnormal Liver Tests in Participants With No Underlying Liver Disease). Such abnormalities would include the following:
 - ALT or AST >8 x the upper limit of normal (ULN)
 - ALT or AST >5 x ULN for more than 2 weeks
 - ALT or AST >3 x ULN **and** total bilirubin >2 x ULN **or** international normalized ratio (INR) >1.5
 - ALT or AST >3 x ULN and symptoms of hepatitis (eg, fatigue, nausea, vomiting, right upper quadrant pain or tenderness, fever, rash, and/or eosinophilia [>5%])

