7.1.2. Conditions to Consider Study Intervention Discontinuation

Discontinuation of a participant's study intervention must be strongly considered under the following conditions:

1. Persistent inadequate response or worsening of UC based on signs, symptoms, and/or laboratory values. If the participant experiences AEs consistent with clinically significant worsening of UC at any time during the study, these events should be evaluated by the investigator and the study medical monitor to decide on discontinuation of study intervention. Discontinuation of study intervention should be considered in participants with clinically significant worsening of UC where continuation of the study intervention is not in the best interest of the participant.
2. The participant develops a serious infection, including but not limited to sepsis or pneumonia.

Note: Any serious infection should be discussed with the medical monitor or designee, and study intervention should be withheld until the clinical assessment is complete.

3. The participant reports suicidal ideation with intention to act (“Ideation level 4”), suicidal ideation with specific plan and intent (“Ideation level 5”), or any suicidal behavior (interrupted suicide attempt, aborted suicide attempt, or preparatory behaviors for making a suicide attempt) on a post-baseline C-SSRS assessment. If a participant can be adequately treated with psychotherapy and/or pharmacotherapy based on an evaluation by a mental health professional, then the participant, at the discretion of the investigator, may be continued with treatment if agreed to by the medical monitor or designee. Discussion of such participants with the medical monitor or designee is required.
4. The participant develops a severe injection-site reaction or AE temporally associated with infusion.
5. Criterion deleted per Amendment 1.

If a participant discontinues study intervention for any reason before the end of the treatment period, assessments should be obtained as specified in the SoA (Section 1.3). Study intervention assigned to the participant who discontinued study intervention may not be assigned to another participant. Additional participants will not be entered.

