- Provides the dates and doses of the failed maintenance therapy with infliximab, adalimumab, golimumab, vedolizumab, or approved biosimilars.
- Documents that the participant had recurrence of UC disease activity despite maintenance therapy with infliximab, adalimumab, golimumab, vedolizumab, or approved biosimilars.

Examples of acceptable documents include medical records, letter provided by a referring physician, or other “reason for referral” documents (eg, insurance authorization form).

III. Current or prior intolerance to therapy with infliximab, adalimumab, golimumab, vedolizumab, or approved biosimilars.

Eligible participants must satisfy criteria A and B.

A. Have had an adverse reaction that meets 1 of the following 3 criteria: 1) significant acute infusion/administration reaction; 2) significant delayed infusion/administration reaction (eg, delayed hypersensitivity or serum-sickness-like reaction); or 3) significant injection site reaction. Definitions of these 3 criteria are provided below.

Adverse reactions must have followed ≥ 1 dose of infliximab, adalimumab, golimumab, vedolizumab, or approved biosimilars and, in the treating physician’s opinion, precluded continued use of the therapy.

1) A significant acute infusion/administration reaction is defined as an adverse reaction that was:

- Manifested through ≥ 1 of the following symptoms.
 - a. Fever (ie, temperature greater than 100°F [38°C])
 - b. Chills or rigors
 - c. Pruritis
 - d. Rash
 - e. Flushing
 - f. Urticaria or angioedema
 - g. Respiratory distress (eg, dyspnea, chest pain or tightness, shortness of breath, wheezing, stridor)
 - h. Clinical hypotension (eg, pallor, diaphoresis, faintness, syncope), blood pressure < 90 mm Hg systolic and 60 mm Hg diastolic, or a systemic or orthostatic drop in systolic blood pressure > 20 mm Hg.

and

- Occurred ≤ 24 hours after infusion/administration of infliximab, adalimumab, golimumab, vedolizumab, or approved biosimilars.

and

- Was considered related to the infusion/administration of infliximab, adalimumab, golimumab, vedolizumab, or approved biosimilars.

2) A significant delayed infusion/administration reaction is defined as an adverse reaction that:

- Was manifested through 1 or more of the following symptoms:

- a. Myalgias
- b. Arthralgias
- c. Fever (ie, temperature greater than 100°F [38°C])
- d. Malaise
- e. Rash

and

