- Occurred >24 hours and <15 days after infusion/administration of infliximab, adalimumab, golimumab, vedolizumab, or approved biosimilars.

and

- Was considered related to the infusion/administration of infliximab, adalimumab, golimumab, vedolizumab, or approved biosimilars.

3) A significant injection site reaction is defined as an adverse reaction that:

- Was manifested through 1 or more of the following symptoms:

- a. Significant bruising
- b. Erythema
- c. Hemorrhage
- d. Irritation
- e. Pain
- f. Pruritus
- g. "Injection site reaction"

and

- Occurred within 24 hours of an SC injection of adalimumab, golimumab, vedolizumab, or approved biosimilars.

and

- Was considered related to the injection.

B. Have documentation available to the investigator that meets the following 2 requirements:

- Provides the date of discontinuation of infliximab, adalimumab, golimumab, vedolizumab, or approved biosimilars.
- Documents that the participant had intolerance to infliximab, adalimumab, golimumab, vedolizumab, or approved biosimilars.

Examples of acceptable documents include medical records, letter provided by a referring physician, or other “reason for referral” documents (eg, insurance authorization form).

10.3. Appendix 3: Definition of Inadequate Initial Response, Loss of Response, or Intolerance to Tofacitinib

The criteria for inadequate initial response, response followed by loss of response, or intolerance to tofacitinib are described in items I, II, and III, below.

I. Inadequate initial response to at least 8 weeks of induction therapy with tofacitinib (primary nonresponse)

Eligible participants must satisfy criteria A, B, and C.

- A. Have received induction therapy with tofacitinib 10 mg by mouth (PO) twice daily (or other approved dose regimen) for at least 8 weeks**

AND

- B. Did not initially respond to induction therapy with tofacitinib, as evidenced by the presence of at least 1 of the following signs or symptoms related to persistence of ulcerative colitis (UC), as assessed by a treating physician:**

- Lack of improvement or worsening in stool frequency
- Lack of improvement or worsening in rectal bleeding
- Lack of improvement or worsening in daily abdominal pain
- Lack of improvement or worsening in urgency
- Lack of improvement or worsening in the endoscopic appearance of the colonic mucosa

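### The mandatory stop for serum-sickness-like reactions names only injections, so as written it cannot apply after the three IV-only induction doses

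*Protocol*

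**What the plan says.** Section 7.1.1 of the protocol lists the conditions under which study intervention must be discontinued. Three matter here.

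- Criterion 2 applies to any route. It requires a stop when the investigator believes, for safety or tolerability reasons, that "it is in the best interest of the participant to discontinue study intervention".
- Criterion 8 begins "The participant has a serious adverse reaction that is related to an injection or an infusion resulting in bronchospasm" and also covers symptomatic hypotension. It names both routes.
- Criterion 9 covers myalgia and/or arthralgia with fever and/or rash that is "suggestive of serum sickness and not representative of signs and symptoms of other recognized clinical syndromes", with onset "occurring 1 to 14 days after an injection of study intervention". It names one route.

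Section 7.1.2 lists conditions under which stopping must be strongly considered but is not required. Item 4 reads "The participant develops a severe injection-site reaction or AE temporally associated with infusion".

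Sections 6.1.1.1 and 6.1.2 give three IV doses at Weeks I-0, I-4 and I-8 in both induction studies, with no SC dose at those visits.

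**The concern.** Two adjacent mandatory stopping rules differ in the routes they name, and the one for delayed reactions omits the only route used for the first three doses. An investigator who diagnosed a serum-sickness-like reaction after an induction infusion would find that the named rule does not bar the next infusion. The same reaction after an SC dose would require stopping. What is at stake is participant safety and consistent application of the rule across sites.

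The result is also uneven within the trial. Placebo nonresponders who cross over to guselkumab at Week I-12 receive active infusions with a placebo SC injection at the same visit to keep the blind. Placebo is itself study intervention under Section 6.1, so that injection brings them under criterion 9. Participants randomized to guselkumab receive their three active infusions at I-0 to I-8 without that cover. The visible text gives no safety reason for the difference.

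**Working it through.** The documents state no figure on this point, so the check compares wording and then timing.

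**Does injection include infusion in this protocol?** The usage says not. Section 6.4 has separate recording requirements for the two routes: start and stop times and volume for IV infusions, whereas "for SC injections, this will include date and time of SC injection". Section 8.2.7 defines injection-site reactions as SC. Section 8.2.9 defines infusion-associated adverse events as those during, or within 1 hour after, an IV infusion. Section 7.1.2 item 4 keeps the two apart, and criterion 8 names both.

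**Could an SC injection fall early enough for criterion 9 to apply?** The inputs are the visit windows in footnote a of Table 1 (I-4 and I-8 ± 4 days, I-12 ± 3 days) and the 14-day upper limit in criterion 9. I assume the I-0 dose is given on the day of randomization, counted as day 0.

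| IV dose | Latest day of dose | Window closes (+14) | Earliest next dose | Gap |
|---|---|---|---|---|
| I-0 | 0 | 14 | I-4: 28 − 4 = 24 | 24 − 14 = 10 days |
| I-4 | 28 + 4 = 32 | 46 | I-8: 56 − 4 = 52 | 52 − 46 = 6 days |
| I-8 | 56 + 4 = 60 | 74 | I-12: 84 − 3 = 81 | 81 − 74 = 7 days |

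The first SC injection is at I-12 for nonresponders, or at M-0 for responders, which may be the same day as I-12 but not before it. Day 81 is therefore the earliest SC dose. No injection precedes, or falls within, any of the three windows, so criterion 9 as written is not met after any of these doses. The smallest gap before the next dose is 6 days, so a rule covering infusions could act before re-dosing.

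**Does another rule make stopping mandatory once the diagnosis is made?**

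- Criterion 8 needs bronchospasm requiring ventilatory support, or symptomatic hypotension. A reaction of joint pain, fever and rash need not meet it.
- Section 7.1.2 item 4 is advisory. With the 1-hour definition in Section 8.2.9, a reaction starting a day or more after the infusion is outside its infusion limb.
- Hypersensitivity observation (Section 8.2.8) and adverse event review at each visit (Table 1) detect events but do not bar the next dose.
- Criterion 2 does require a stop, but only on a best-interest judgement.

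**Reach.** Table 6 plans 336 guselkumab participants with a modified Mayo score of 5 to 9 in Induction Study 2.

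- Active infusions at I-0, I-4 and I-8: 336 × 3 = 1,008.
- Of these, followed by another IV infusion within the same three-dose course: 336 × 2 = 672.
- Lower bound: 0, because the documents do not give the number still to be administered.

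Induction Study 1 is not counted, since Section 4.1 states that its enrolment was complete before Amendment 2.

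**The case against.** The strongest reply is that criterion 2 already covers the case. It sits in the same mandatory list, applies to any route and gives an adverse event as its example. Criterion 9 also depends on clinical judgement, so an investigator who has just diagnosed serum sickness has a clear basis to stop under criterion 2. The remaining gap is an investigator who makes that diagnosis after an infusion and still judges further dosing to be in the participant's interest. This stands, and it makes the practical effect small. It does not remove the difference between the routes: under criterion 9 the diagnosis alone requires stopping, while under criterion 2 a second judgement is needed.

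Exposure is also limited to three doses. At I-12, I-16 and I-20 every infusion is accompanied by an SC injection, and all maintenance and extension dosing is SC. That is correct.

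The reach figure is a ceiling. The documents point towards its low end: protocol Section 9.2.2 and SAP Section 1.2 describe some enrolment in the past tense, and SAP Amendment 2 is dated 08 September 2023. The count is also of active infusions only. A stopping rule is applied blind, so placebo infusions would come under it too, and participants with a modified Mayo score of 4 are left out. The figure should be read with those limits.

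Appendix 2 of the protocol shows that the sponsor recognises a "significant delayed infusion/administration reaction (eg, delayed hypersensitivity or serum-sickness-like reaction", with overlapping symptoms and nearly the same window ("Occurred >24 hours and <15 days after infusion/administration of infliximab" and the other listed agents). But that appendix defines past intolerance to other biologics for eligibility, and any one of its listed symptoms suffices. It shows that the protocol recognises delayed reactions after infusion. It does not show what was intended for guselkumab.

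Finally, the guselkumab risk and mitigation rows in Section 2.3.1 are redacted and may contain further safeguards. They would not change the wording of criterion 9.

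**Conclusion.** The concern holds. As written, the mandatory serum-sickness stop cannot be triggered after the doses at I-0, I-4 and I-8, and no other visible rule makes stopping mandatory on that diagnosis alone. This rests on reading injection as SC, which the protocol's own usage supports, and on visits falling within their stated windows.

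The effect is limited. Criteria 2 and 8 and routine safety review still protect participants, the expected harm cannot be calculated, and a correction would reach between 0 and 1,008 planned active infusions in Induction Study 2. No endpoint, analysis population, power or error rate is affected. The contrast with criterion 8, and the cover that crossover participants gain only through a blinding injection, look more like a drafting omission than a deliberate choice, but the documents do not settle this. It should be corrected because the change is nearly free and the rule is a safety rule.

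**What to change.** Reword the timing clause of criterion 9 so that the reaction counts when it starts 1 to 14 days after *an injection or infusion* of study intervention, matching criterion 8.

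If infusions were always meant to be covered, a protocol clarification communication under Appendix 8 (Section 10.8) is enough, with the text carried into the next amendment. If the coverage is new, it changes study conduct and needs an amendment with IEC/IRB approval.

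The cost is two added words, with no new procedure, visit or data item, plus the approval step if an amendment is used. The sponsor should first confirm whether any IV induction doses remain to be given, since only those can benefit.

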7.1.2. Conditions to Consider Study Intervention Discontinuation

Discontinuation of a participant's study intervention must be strongly considered under the following conditions:

1. Persistent inadequate response or worsening of UC based on signs, symptoms, and/or laboratory values. If the participant experiences AEs consistent with clinically significant worsening of UC at any time during the study, these events should be evaluated by the investigator and the study medical monitor to decide on discontinuation of study intervention. Discontinuation of study intervention should be considered in participants with clinically significant worsening of UC where continuation of the study intervention is not in the best interest of the participant.
2. The participant develops a serious infection, including but not limited to sepsis or pneumonia.

Note: Any serious infection should be discussed with the medical monitor or designee, and study intervention should be withheld until the clinical assessment is complete.

3. The participant reports suicidal ideation with intention to act (“Ideation level 4”), suicidal ideation with specific plan and intent (“Ideation level 5”), or any suicidal behavior (interrupted suicide attempt, aborted suicide attempt, or preparatory behaviors for making a suicide attempt) on a post-baseline C-SSRS assessment. If a participant can be adequately treated with psychotherapy and/or pharmacotherapy based on an evaluation by a mental health professional, then the participant, at the discretion of the investigator, may be continued with treatment if agreed to by the medical monitor or designee. Discussion of such participants with the medical monitor or designee is required.
4. The participant develops a severe injection-site reaction or AE temporally associated with infusion.
5. Criterion deleted per Amendment 1.

If a participant discontinues study intervention for any reason before the end of the treatment period, assessments should be obtained as specified in the SoA (Section 1.3). Study intervention assigned to the participant who discontinued study intervention may not be assigned to another participant. Additional participants will not be entered.

7.2. Participant Discontinuation/Withdrawal From the Study

A participant will be withdrawn from the study for any of the following reasons:

- Lost to follow-up (see Section 7.3)
- Withdrawal of consent
- Death
- Sponsor decision (eg, participating in any other clinical study with an investigational agent)

When a participant withdraws before completing the study, the reason for withdrawal is to be documented in the eCRF and in the source document. Participants who terminate study participation will not be required to return for any follow-up assessments; however, these participants should complete the safety and efficacy evaluations specified in the SoA (Section 1.3) at the time they terminate study participation. If the reason for withdrawal from the study is withdrawal of consent, then no additional assessments are allowed.

Withdrawal of Consent

A participant declining to return for scheduled visits does not necessarily constitute withdrawal of consent. Alternate follow-up mechanisms that the participant agreed to when signing the consent form apply as local regulations permit.

